6.11 Criteria for Patient Removal

Diagnosis of >3 bone and/or soft tissue metastases on entry imaging studies before SBRT/SABR. PSA >50 ng/ml before SABR. Progression as defined in section 9.5.5.

Radium-223 administration may be delayed by no more than four weeks for recovery of adverse events. In case of a treatment delay greater than four weeks, treatment should be discontinued. It is important to note that in general (unless otherwise agreed), in cases where study drug has been ordered, the time window is reduced to -3 days to + 3 days, due to decay. If administration has to be postponed more than 3 days after drug has been ordered, replacement of the drug order is required. Dose reduction for radium-223 will not be permitted and subjects with any toxicity requiring radium-223 dose reduction must discontinue radium-223 treatment.

Any toxicity requiring radium-223 discontinuation will be recorded as an AE in the subject's medical record and on the CRF.

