9.5.5 Clinical Response Parameters

Progression is a composite endpoint defined from the Prostate Cancer Working Group 2 (PCWG2) criteria for metastatic castrate resistant prostate cancer (mCRPC) (75) and our previous trials in a population of men with biochemical failure without metastases (72-74). Progression will be defined as either: 1) a $\geq 25\%$ increase in PSA from nadir (and by ≥ 2 ng/mL), requiring confirmation ≥ 4 weeks later (PCWG2 criteria); and/or, 2) clinical/radiographic-progression defined as symptomatic progression (worsening disease-related symptoms or new cancer-related complications), or radiologic progression (on CT scan: $\geq 20\%$ enlargement in sum diameter of soft-tissue target lesions [RECIST 1.1 criteria]; on bone scan: ≥ 1 new bone lesions), initiation of ADT or death due to any cause, whichever occurs first. Death is considered a severe adverse event here.

Progression Free Survival (PFS) is defined as the time from starting treatment to the time of progression as defined above. Subjects who do not progress will be censored at the time of the last contact.

ADT Free Survival (ADT-FS) is defined as the time from starting treatment to the time of initiation of palliative ADT. ADT will typically be initiated on tumor progression and/or development of new metastases. Subjects who do not start ADT will be censored at the time of the last contact.

Time to Progression (TTP) is defined as the time from starting treatment to the time of first documented tumor progression or new lesions by CT and/or bone scan or initiation of ADT. Subjects who do not progress will be censored at the time of the last contact. In addition, death from any cause will also be censored.

Time to New Metastasis (TNM) is defined as the time from starting treatment to the time of a new documented tumor metastasis by CT and/or bone scan. Subjects who do not progress will be censored at the time of the last contact.

Overall Survival (OS) is defined as the time from starting treatment until death due to any cause. For subjects who do not die, time to death will be censored at the time of last contact.

Locoregional Control (LRC) is defined as the time from starting treatment until local and/or regional relapse is documented

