14.2 Sample Size/Accrual Rate/Follow-Up

The primary endpoint will be progression-free survival (PFS). Data from STOMP and ORIOLE on this patient population indicate that $\geq 50\text{-}60\%$ would show progression as defined above within a 12-month period from SABR, and a median PFS around 10 months. (72-74). We hypothesize that the addition of radium-223 will be able to reduce the risk of progression by 50%. A sample size using a 1:1 randomization scheme of 30 patients per arm will provide 80% power to detect an increase of median PFS from 10 months to 20 month (corresponding to hazard ratio 0.5) with type I error = 0.1, using one-sided log-rank test. The calculation assumes 18 months of accrual time with an additional follow-up of 12 months after the last patient is randomized. To account for 5% early drop out, we will randomize a total of 64 patients (32 per arm).

There will be no interim analysis for futility, since the progression endpoint will not have been reached by a meaningful number of patients before full accrual.

Follow-up (Every 3-6 months for 24 months or until death)

Patients will be followed for 2 years after Day One of trial or until death. Patients withdrawn from the study because of AEs will be followed until the adverse event has either resolved or stabilized. Reasons for premature withdrawal should be determined and noted.

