14.5 Analysis of Secondary Objectives

- For safety analysis, adverse events will be summarized by type and grade.
- Kaplan-Meier (KM) estimates will be used to summarize ADT-free survival (ADT-FS), time to locoregional progression (TTLP), time to distant progression (TTDP), time to new metastasis (TNM) and duration of response over time. The median PFS, ADT-FS, TTLP, TTDP TNM and duration of response will be reported.
- The efficacy of SABR + Radium-223 in men with oligometastatic disease will also be determined by measuring local control of each lesion at 12-months.

Each metastatic lesion will be considered a target lesion and independently evaluated for response using RECIST 1.1 or bone scan evaluation criteria above. The lesion will be coded as being locally controlled if it is considered stable radiographic disease or if there is evidence of a partial or complete response. Local control assessment will start at three months following randomization and continuous assessment will be pursued during the follow-up period. The proportion of the lesions that have a stable or better response will be estimated using generalized estimating equation.

- Quality of life will be assessed using the Brief Pain Inventory form. An overall score will be calculated pre-treatment and at the time of the 2nd radiologic reassessment. The change in score will be evaluated with a paired t-test.

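### Times to locoregional progression, distant progression and new metastasis are planned as Kaplan-Meier summaries with no competing-event rule; if men who leave for another progression are censored, the failure proportions are overstated

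*Combined protocol and SAP*

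**What the plan says.** - **Estimator.** 14.5 (Analysis of Secondary Objectives): "Kaplan-Meier (KM) estimates will be used to summarize ADT-free survival (ADT-FS), time to locoregional progression (TTLP), time to distant progression (TTDP", with TNM and duration of response in the same list. The summary statistic is the median: "The median PFS, ADT-FS, TTLP, TTDP TNM and duration of response will be reported". No between-arm test is named for these endpoints, and cumulative incidence is not mentioned anywhere.
- **Definitions.** 9.5.5 does not define TTLP or TTDP by those names. The nearest entry is "Locoregional Control (LRC) is defined as the time from starting treatment until local and/or regional relapse is documented", which has no censoring rule. TNM censors men who do not progress at last contact, and says nothing about a man who first progresses in another way, starts ADT or dies. TTP does have such rules: ADT start is an event and death is censored.
- **Leaving the study.** 6.11 lists as a removal criterion "Progression as defined in section 9.5.5", which covers PSA, symptomatic and radiologic progression, ADT start and death. 6.15 lists progressive disease as a reason for which the investigator may withdraw a man.
- **ADT.** 9.5.5: "ADT will typically be initiated on tumor progression and/or development of new metastases".
- **Staying in the study.** 6.10 and 14.2 follow men for two years (14.2: or until death). 6.7.2 schedules imaging at 6 and 12 months for all patients. Study Calendar footnotes R (SABR arm) and U (radium arm) limit the 360-day PSMA PET/CT to men still enrolled. After month 12, imaging is at the treating physician's discretion.

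**The concern.** Each of these endpoints counts one kind of failure, and a man may leave observation because of a different kind. Kaplan-Meier treats a censored man as having the same later risk as those still under observation. If removal for another progression is handled as censoring, the curve describes a setting in which other progressions do not occur. It does not describe the proportion of treated men who have a locoregional or distant failure, which is how most readers would take it.

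The case is clearest for locoregional progression. Section 4.5 calls progression at microscopic metastatic sites the predominant mode after SABR, so a man will often leave for a distant lesion before any local failure is seen. At stake are the descriptive failure percentages and the promised medians.

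**Working it through.** **1. The plan's own figure.** 14.2: "A sample size using a 1:1 randomization scheme of 30 patients per arm will provide 80% power" for an "increase of median PFS from 10 months to 20 month (corresponding to hazard ratio 0.5") "with type I error = 0.1, using one-sided log-rank test". Required events (Schoenfeld): 4(1.282 + 0.842)² / (ln 0.5)² = 37.5, so 38. With exponential PFS, 18 months of uniform accrual and 12 further months, the event probabilities are 0.751 and 0.509. Then 30 × (0.751 + 0.509) = 37.8 events and power is 80.2%. Dropout: 60 / 0.95 = 63.2, so 64 with equal arms. The design figure reproduces. The plan gives no figure for TTLP, TTDP or TNM.

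**2. Inputs for the check.** From 14.2, total progression hazard h = ln 2 / median: 0.0693 per month (SABR) and 0.0347 (radium). Assumptions, not in the documents: constant hazards, independent failure types, the same share s of first progressions due to the type of interest in both arms (so radium halves every type), and censoring at the other progression.

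**3. Formulas.**
- One minus Kaplan-Meier = 1 − exp(−s·h·t)
- Cumulative incidence (CIF) = s·(1 − exp(−h·t))

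**4. Share 20%, 12 months.**
- SABR: 1 − exp(−0.2 × 0.0693 × 12) = 15.3%; CIF = 0.2 × 0.565 = 11.3%; excess 4.0 points.
- Radium: 1 − exp(−0.2 × 0.0347 × 12) = 8.0%; CIF = 0.2 × 0.340 = 6.8%; excess 1.2 points.
- Yardstick: with 32 men, the SE of the SABR incidence is √(0.113 × 0.887 / 32) = 5.6 points, so the SABR excess is about 0.7 SE.

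**5. Other shares, 12 months** (excess taken before rounding):

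| Share | SABR: 1−KM v CIF | Excess | Radium: 1−KM v CIF | Excess |
|---|---|---|---|---|
| 10% | 8.0 v 5.6 | 2.3 | 4.1 v 3.4 | 0.7 |
| 20% | 15.3 v 11.3 | 4.0 | 8.0 v 6.8 | 1.2 |
| 30% | 22.1 v 16.9 | 5.1 | 11.7 v 10.2 | 1.5 |
| 50% | 34.0 v 28.2 | 5.8 | 18.8 v 17.0 | 1.8 |
| 70% | 44.1 v 39.5 | 4.6 | 25.3 v 23.8 | 1.4 |
| 90% | 52.7 v 50.8 | 1.9 | 31.2 v 30.6 | 0.6 |

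At 24 months and a 20% share, SABR is 28.3% v 16.2% (+12.1 points) and radium 15.3% v 11.3% (+4.0). These are illustrative only, because imaging after month 12 is discretionary.

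**6. Medians.** The Kaplan-Meier median is the PFS median divided by s: 10/0.5 = 20 and 20/0.5 = 40 months at a 50% share; 50 and 100 months at 20%, which is beyond two years in both arms. CIF cannot exceed s, so with a share of 50% or less it has no median. At 70% the medians are 14.3 v 28.6 months by Kaplan-Meier and 18.1 v 36.1 by CIF.

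**7. If men are followed past the other progression.** A simulation for the SABR arm (share 20%, 12 months), with the later hazard multiplied by an assumed 1, 0.5 or 0.25, gives an any-time incidence of 15.3%, 13.3% or 12.3%. With that follow-up in hand, Kaplan-Meier estimates this quantity and does not overstate it.

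**8. If radium leaves locoregional hazard unchanged but total hazard still halves.** The 20% SABR share becomes 40% in the radium arm. At 12 months one minus Kaplan-Meier is 15.3% in both arms; CIF is 11.3% v 0.4 × 0.340 = 13.6%. The excess is still larger under SABR (4.0 v 1.7 points), but Kaplan-Meier shows no radium benefit.

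**The case against.** The strongest reply is that censoring at another progression is inferred, not written. 6.10 and 14.2 follow men for two years, 6.7.2 images all patients at 6 and 12 months, 14.5 assesses local control throughout follow-up, and withdrawal under 6.15 is optional. If men stay under observation, the gap is a difference of estimand, not a bias. This stands as a condition on the point. It does not remove the point, because 6.11 lists progression as a removal criterion, the 360-day PSMA PET/CT is only for men still enrolled, and nothing says whether a man remains at risk. It is also fair that these are descriptive secondary summaries, and that lesion-level local control is estimated separately by GEE.

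A reader might infer more than the documents support:
- *That another type usually comes first for all three endpoints.* Section 4.5 supports this for locoregional failure. It points the other way for TTDP and TNM; an earlier PSA progression is possible, but no figure is given.
- *That a PSA rise puts a man on ADT.* 9.5.5 ties ADT to tumor progression or new metastases, and 6.12 gives biochemical progression as PSA above 50 ng/ml. A 25% rise does not, as written, lead to ADT.
- *That the method exaggerates the benefit of radium.* 14.2 gives only an overall PFS hazard ratio. The inference needs radium to act on all failure types, and step 8 shows a case where no false benefit appears.

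**Conclusion.** The point holds conditionally. Kaplan-Meier is the only planned method for TTLP, TTDP and TNM, there is no competing-event rule, and removal at progression is provided for. If men who leave for another progression, or who die, are censored, one minus Kaplan-Meier overstates the proportion with each failure type. At 12 months and a 20% locoregional share the excess is 4.0 points (SABR) and 1.2 (radium). Over shares of 10% to 90% it is 1.9 to 5.8 and 0.6 to 1.8 points. This is moderate against the sampling error of 32 men per arm.

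The shares, constant hazards and independence are assumptions. The larger SABR excess is on the absolute scale and depends on radium lowering the total progression hazard; with no radium effect and equal shares the arms are equal. An exaggerated radium benefit is not established. The primary PFS analysis is unaffected, since every progression type and death is an event there.

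**What to change.** In 14.5, report TTLP, TTDP and TNM as Aalen-Johansen cumulative incidence by arm, mainly at 12 months. Treat death, and end of follow-up because of another progression type, as competing events. Give cause-specific hazard ratios if the arms are compared. Keep Kaplan-Meier for PFS.

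In 9.5.5, define TTLP and TTDP and give each endpoint a rule for another progression, ADT start and death. Reconcile 6.11 and 6.15 with the two-year follow-up in 6.10 and 14.2, and state whether men stay at risk after another progression or ADT start. If they do, label the curves as failure at any time and add a sensitivity analysis with ADT start as a competing event.

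The cost is SAP wording, a standard estimator and a little more analysis; the trial already has to record progression type, ADT start and death for PFS. Reported failure percentages will be lower, and some medians may not be reached. Sample size and the primary analysis do not change.

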1. PROTOCOL SYNOPSIS

TITLE	A phase II randomized trial of R adium-223 and SABR V ersus SABR for oligom E static prostate ca N cerS (RAVENS)
STUDY PHASE	Phase II
INDICATION	Men with oligometastatic disease (<3 mets) and at least one bone metastasis
INVESTIGATIONAL PRODUCT	Radium-223 (Xofigo®) is an alpha-emitting radioisotope developed by Algeta ASA. Radium-223 is indicated for treatment of men with castrate-resistant prostate cancer (CRPC) with symptomatic bone metastases and no known visceral metastatic disease. The approved dose and schedule of radium-223 is 50 kBq (or 1.35 microcurie) (55 kBq/kg (or 1.49 microcurie)) after implementation of the NIST update) per kg body weight intravenous (IV) infused at 4 week interval for 6 injections
PRIMARY OBJECTIVES	
• To assess progression-free survival of men who have oligometastatic prostate cancer after randomization to stereotactic ablative radiation therapy (SABR) versus SABR and Radium-223
SECONDARY OBJECTIVES	
• To assess the toxicity of SABR + Radium-223 in patients with oligometastatic disease• To determine local control at 12-months after SABR versus SABR + Radium-223 in patients with oligometastatic disease• To assess time to locoregional progression, time to distant progression, time to new metastasis and duration of response• To assess ADT-free survival after randomization to SABR versus SABR + Radium-223• To assess quality of life following SABR versus SABR + Radium-223

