3.3 Secondary Objectives

To assess the toxicity of SABR + Radium-223 in patients with oligometastatic disease.

To determine local control at 12-months after SABR + Radium-223 in patients with oligometastatic disease.

To assess time to locoregional progression, time to distant progression, time to new metastasis and duration of response after randomization to SABR *versus* SABR + Radium-223.

To assess ADT-free survival after randomization to SABR *versus* SABR + Radium-223.

To assess quality of life following completion of SABR + Radium-223.

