Conventional moderate dose radiation for metastatic disease is given primarily for palliation. Recent advancements in radiation delivery now make it possible to image and treat precisely within any anatomical region of the body (6, 7). As a result, the capacity to deliver tumor killing radiation doses in a single or few (1-5) outpatient radiation treatments is now possible (8-12). In addition, by minimizing the irradiation of surrounding healthy tissue, it should also be possible to decrease the rate of complications. Intracranial stereotactic body radiation therapy (SBRT) [also known as stereotactic ablative radiation therapy (SABR)] has been shown to be a highly effective treatment for brain metastases (13). Data suggests that selective small extracranial tumors (either primary or metastatic tumors) may be effectively controlled by similar focal high-dose SBRT/SABR. There is an increasing experience with extracranial SBRT as effective local therapy for metastatic lesions. Local control in excess of 75% has been reported for metastatic tumors of the spine, lung and liver, which is significantly higher than standard conventional moderate dose radiation (9, 11, 12, 14)(15-27). Toxicity has been minimal in multiple U.S., European and Japanese trials of extracranial stereotactic radiotherapy to the lung, liver, spine, pelvis and abdomen despite the use of very high biological equivalent doses for patients with both organ confined and metastatic cancer.

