metastases represent the major metastatic site (>90%) in men with rising PSA following primary treatment for their prostate cancer.

The prospective randomized phase II STOMP trial reported the ability of metastasis-directed therapies (MDT), primarily SABR, to forestall initiation of ADT in men with hormone-sensitive metastatic prostate cancer with three or fewer detectable metastases. STOMP showed ADT-free survival was lengthened in men randomized to MDT versus observation. The authors reported median ADT-free survival of 21 vs 13 months for the MDT and surveillance arms, respectively. All patients for whom ADT was initiated due purely to local (n = 6) or symptomatic (n = 3) progression were from the surveillance arm, underlining the high efficacy of MDT for local control of individual metastatic lesions. Nearly equal numbers of men in the MDT (n = 19) and surveillance (n = 16) arms received ADT due to polymetastatic progression, suggesting there may have been distinct subpopulations within this oligorecurrent STOMP cohort, i.e. those who had oligometastatic disease and where MDT impacted future macroscopic metastatic colonization versus those who had so-called “OligoVisible” polymetastatic disease already beyond the practical reach of MDT alone.

Our own prospective randomized phase II ORIOLE trial is similar to STOMP and nearly completed. Although preliminary, our data show a significant ability of SABR to delay progression in men with oligorecurrent prostate cancer. In addition, these combined preliminary data suggest that progression at microscopic metastatic sites is the predominant mode of progression in men with oligorecurrent prostate cancer treated with SABR.

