14.1.2 Secondary Objectives

- To describe the toxicity of SABR and SABR + Radium-223 delivered for the population enrolled using grading with CTCAE v. 4.0
- To determine local control at 12-months after SABR and SABR + Radium-223 in patients with oligometastatic disease.

- To assess time to locoregional progression, time to distant progression, time to new metastasis and duration of response after randomization to SABR *versus* SABR + Radium-223.
- To assess ADT-free survival (ADT-FS) of this patient population after randomization defined as the time interval between the day of randomization and the initiation of ADT. ADT will typically be initiated on progression and/or development of new metastases.
- To assess quality of life following SABR *versus* SABR + Radium-223 arms. Brief Pain Inventory form which will be filled out by the patient at the treatment response intervals outlined above.

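### Section 14.5 draws efficacy of SABR + Radium-223 from a lesion-control proportion and specifies no contrast with the randomised SABR arm

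*Combined protocol and SAP*

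**What the plan says.** Section 14.5 (Analysis of Secondary Objectives) opens its local-control bullet with "The efficacy of SABR + Radium-223 in men with oligometastatic disease will also be determined by measuring local control of each lesion at 12-months". It then defines the lesion outcome: "The lesion will be coded as being locally controlled if it is considered stable radiographic disease", or if it shows a partial or complete response. The method is one sentence: "The proportion of the lesions that have a stable or better response will be estimated using generalized estimating equation". No arm effect, difference, odds ratio, confidence interval, test or reference rate follows.

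The objective behind this analysis is worded in three ways:

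- **Synopsis:** "To determine local control at 12-months after SABR", continuing with *versus* SABR + Radium-223. This is comparative.
- **Section 3.3:** "To determine local control at 12-months after SABR + Radium-223 in patients with oligometastatic disease". Only the combination is named.
- **Section 14.1.2:** "To determine local control at 12-months after SABR and SABR + Radium-223 in patients with oligometastatic disease". Both arms are named, but no comparison is stated.

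The synopsis (Study Design) gives SABR to all men. On what SABR alone achieves, section 4.2 says "Local control in excess of 75% has been reported for metastatic tumors of the spine, lung and liver", and section 4.5 describes the earlier randomised trial of metastasis-directed therapy as "underlining the high efficacy of MDT for local control of individual metastatic lesions". Section 4.5 also describes local control after SBRT/SABR as very high in selected patients, without a figure.

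**The concern.** Local control of a treated lesion is what SABR is meant to deliver, and SABR is given in both arms. A high proportion in the combination arm is therefore expected even if radium-223 does nothing for the treated lesions. Section 14.5 nevertheless presents that proportion as the means of determining the efficacy of the combination. A report that followed the text literally could credit SABR's effect to SABR + Radium-223 and leave the comparative objective in the synopsis unanswered, although a randomised control arm is available to answer it.

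**Working it through.** **1. The plan's own figures.** The plan gives no target, null rate, difference or power for local control. Its only design figure is for PFS (section 14.2): medians of 10 and 20 months, one-sided alpha 0.10, 80% power, 18 months of accrual plus 12 of follow-up.

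- Events needed (Schoenfeld): 4(1.2816 + 0.8416)² / (ln 0.5)² = 37.5, so 38.
- Event probability per arm, exponential PFS and uniform accrual: 1 − [exp(−12λ) − exp(−30λ)] / (18λ), with λ = ln 2 / median. This gives 0.751 and 0.509.
- Expected events with 30 per arm: 30 × (0.7513 + 0.5092) = 37.8. Power: Φ(√37.8 × 0.6931/2 − 1.2816) = 0.802.
- Drop-out: 60 / 0.95 = 63.2, so 64.

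The PFS design reproduces. It provides no basis for the local-control analysis.

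**2. What the proportion in section 14.5 can identify.** Let *p* be 12-month lesion control under SABR alone and *d* the change from adding radium-223. The text does not say which lesions enter the proportion, so there are three readings:

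| Reading | Quantity estimated | Is *d* identified? |
|---|---|---|
| Combination arm only (as in section 3.3) | p + d | No: one number, two unknowns |
| Both arms pooled, equal lesion numbers | p + d/2 | No, same reason |
| Each arm separately (as section 14.1.2 could imply) | p and p + d | Only by subtraction, which the plan does not call for and for which it gives no interval |

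For example, 90% control in the combination arm fits p = 0.90 with d = 0 equally as well as p = 0.80 with d = 0.10. This holds at any observed value and does not depend on the background figure of over 75%.

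**3. Precision of the missing contrast.** Assumptions, none stated in the documents: one, two or three lesions in 50%, 30% and 20% of men; within-man correlation ρ of 0.1 to 0.3; control of 85% to 95% in both arms; 12-month data on all 32 men per arm (32 is from section 14.2).

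- Mean lesions per man: 0.5×1 + 0.3×2 + 0.2×3 = 1.7.
- Effective lesions per arm: 32 × 1.7² / (1.7 + 1.8ρ). The 1.8 is the mean of m(m − 1) over men with m lesions: 0.3×2 + 0.2×6. This gives 49.2 at ρ = 0.1 and 41.3 at ρ = 0.3.
- 95% half-width of the difference: 1.96 × √[2p(1 − p) / effective lesions].

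| Control in both arms | ρ = 0.1 | ρ = 0.3 |
|---|---|---|
| 75% | 17.1 points | 18.7 points |
| 85% | 14.1 | 15.4 |
| 90% | 11.9 | 12.9 |
| 95% | 8.6 | 9.4 |

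The half-width is about 9 to 15 points for control of 85% to 95%, and 17 to 19 points at 75%. With 30 men per arm, close to the plan's own 5% loss, each figure is multiplied by √(32/30) = 1.03.

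**The case against.** The strongest reply is that a comparison is plainly intended. Two of the three objective statements name both arms, and the method sentence in section 14.5 is not restricted to the combination arm, so one could expect a proportion per arm, side by side. That stands to this extent: a reader might infer that the control arm is excluded from the analysis, and the documents do not support that. What they show is a comparison left unspecified in section 14.5 and absent from section 3.3.

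A second reply is that section 14.5 contains no decision rule. This is also correct. A reader might take the background figure of over 75% as a benchmark and work out how often an ineffective drug would pass it. But the protocol does not use that figure as a threshold, and it refers to spine, lung and liver metastases rather than prostate bone lesions. Any such probability would belong to a rule the reader had supplied.

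Third, the gap is not unique. The time-to-event secondary endpoints receive only Kaplan-Meier summaries and medians, and quality of life a paired t-test. True, but those bullets do not claim to determine efficacy of the combination; this one does. That separates it from ordinary brevity.

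Finally, the word *also* in the sentence marks the analysis as supplementary. That limits the consequence but does not make the inference sound.

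**Conclusion.** The concern holds for the analysis text. As written, section 14.5 bases an efficacy statement about SABR + Radium-223 on a proportion that cannot separate radium-223 from SABR, and it does not carry out the comparison in the synopsis objective. That conclusion is logical and needs no assumed control rate; it rests only on SABR being given to all men in both arms.

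A reader might go further and infer that the trial's main efficacy conclusion is compromised. It is not: section 14.4 compares PFS between arms by log-rank in all randomised men, and that analysis is untouched. Nor can a false-efficacy rate be stated for this plan.

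The only sizes given are for the contrast that should be added: a 95% half-width of about 9 to 15 points under the assumptions listed, wider if control is lower or 12-month lesion data are incomplete. The data could bound a radium-223 effect on local control but would rarely show a small one. The change should be made, as a correction to a secondary analysis.

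**What to change.** In section 14.5, replace both the efficacy sentence and the GEE sentence. Replacing only the first would leave the proportion without a contrast. Suggested text:

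> 12-month lesion control will be estimated in each arm and compared by a GEE with lesion as the unit, man as the cluster and randomised arm as covariate. The between-arm difference in proportions (or odds ratio) will be reported with a 95% CI, using a small-sample-corrected robust variance, or a man-level bootstrap or exact method if an arm has few or no failures. Within-arm proportions are descriptive and will not be used to conclude efficacy of the combination. This comparison is exploratory.

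State the link function and which effect measure is reported; either measure answers the objective. Align sections 3.3 and 14.1.2 with the *versus* wording of the synopsis.

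The cost is wording and one model term. Sections 6.7.2 and 9.1 already plan imaging at 6 and 12 months for all patients, so no new men, visits or scans are needed. The downside is a less favourable-looking result: a wide interval in place of a single high percentage.
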